When a patient is identified having a highly suspicious pigmented lesion, the diagnosis of melanoma is confirmed with an excisional biopsy (a biopsy that grossly includes a narrow rim of uninvolved tissue), part of the normal standard of care. When present, demonstration of a robust population of TILs in the biopsied specimen is a strong indicator of a natural immune response. We aim to assess the utility of treating highly suspicious pre-metastatic lesions in a randomized, placebo-controlled, trial of intralesional IL-2. We hypothesize that a "proactive" pre-treatment strategy with IL-2 will boost local immune response to suspicious lesions by stimulating a robust TIL response that could ultimately prevent distant metastasis. We believe this to be the future of melanoma therapy.

We aim to include 20 local participants over the next 24 months in a randomized, placebo-controlled, trial of intralesional IL-2 to assess the utility of treating highly suspicious pre-metastatic lesions. Patient consent will be obtained using an NS Health Authority, REB-approved SOP. All patients will have lesions biopsied following standard surgical practice techniques, and will provide blood and urine for analysis. Tissue samples will be assessed for immune system activity, and blood and urine will undergo proteomic and metabolomic analysis.

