#### Participant consent:

Consent will be obtained using an approved NS Health Authority REB protocol. It will be clear to the patient that it is important that they tell their surgeon about any drugs or medicines they are taking or wish to take and that they must also tell their surgeon if they are having any adverse effects. Patients will be allowed to withdraw from the study protocol at any time. It will also be clear that if they withdraw consent, the information about them and their donated tumor tissue that was collected before they left the study will still be used. No new information about them will be collected (and no further testing of donated tumor tissue, blood or urine will be done) without permission.

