#### **Research Plan:**

Clinical Research Plan: Is intralesional pre-treatment of IL-2 in highly suspicious pigmented lesions effective in preventing future melanoma lesion spread and metastasis?

This study is primarily designed to determine if tumor specific immunity can be generated in patients with highly suspicious pigmented lesions in response to intralesional IL-2, and whether

that immunity can confer resistance to melanoma metastasis. Patients will be identified by qualified dermatologists and interviews will be held at the surgery clinic (4th floor Dickson Center) QEII HSC, NSHA.

The standard wait time from consultation to surgical biopsy is up to 4 weeks. We will ensure that patients are seen immediately upon notification from participating dermatologist and all research components of the study are completed within the normally anticipated wait time. Through utilization of this standard wait time, we can potentially affect an immune response using intralesional IL-2, that otherwise could not be achieved after the biopsy is completed. Given that the study is conducted within the normal wait time, it doesn't deviate from the normal standard of care. Following our protocol, patients will receive intralesional injections on Day 1(Week 1 Visit) and Day 8 (Week 2 Visit), and excisional biopsies will be performed on Day 15 (Week 3 Visit), well within the accepted wait time from consultation to biopsy. The intralesional injections and collection of biospecimens beyond the biopsy deviate from but does not delay the normal standard of care. Two additional visits are required in addition to the initial consultation.

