#### How will the data be analyzed:

All study practices and statistical methods are based on the International Conference on Harmonization (IHC) document "Statistical Principles for Clinical Trials." Data will be summarized by treatment group. Baseline characteristic, safety outputs and a total overall column will be included to summarize all subjects. For all baseline, demographic, safety and efficacy outputs data will be summarized by treatment group. In summary tables of continuous variables, the minimum and maximum statistics, the arithmetic mean and median, the 95% confidence interval, standard deviation, and standard error will be presented will to the same number of decimal places as the original data. In summary tables of categorical variables, counts and percentages will be used. The denominator for each percentage will be the number of subjects within the population treatment group unless otherwise specified. All hypothesis testing will be carried out at the 5% (2-sided) significance level unless otherwise specified. P-values will be rounded to three decimal places. P-values less than 0.001 will be reported as <0.001 in tables.

The treatment label for all tables, listings and figures will be:

Treatment	Label
2 treatment cycles of	IL-2
500,000 IU of IL-2 in 0.1	Treatment
mL	
0.1 mL of sterile saline	Placebo
(0.9% m/v)	
All Treatments	Total

Where that any of the statistical methods described herein prove unsuitable during analysis, more appropriate methods will be used. All changes in methodology will be documented in the clinical study report. Additional ad-hoc analyses may be conducted as deemed suitable.

Subject inclusion/exclusion criteria will be determined at baseline visit, and subjects who do not meet all criteria will not be entered into the study. Those subjects deemed eligible to participate will be allocated a 3-digit number at randomization prior to the initial treatment. If a subject is discontinued at any time after entering the study, the Investigator will ensure this does not affect the patient's standard of care. At the patients request all unused biological samples (blood, urine, and core biopsies) will be immediately destroyed. The reasons for withdrawal will be recorded on the CRF and will be included in the final report. Failure to complete both (2) treatment cycles will result in patient removal from the trial.

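### Patients who miss an injection after randomization are removed from the trial, no analysis set is defined, and the plan does not say whether they are assessed or analysed

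*Combined protocol and SAP*

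**What the plan says.** All references are to the combined protocol and SAP.

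- **Order of events.** Under How will the data be analyzed: "Those subjects deemed eligible to participate will be allocated a 3-digit number at randomization prior to the initial treatment". Injections are on Day 1 and Day 8 and the excision is on Day 15 (Research Plan).
- **Removal rule.** The same analysis section says: "Failure to complete both (2) treatment cycles will result in patient removal from the trial".
- **Population.** The nearest text to an analysis set is: "The denominator for each percentage will be the number of subjects within the population treatment group unless otherwise specified". That population is not defined, and no intention-to-treat, per-protocol or safety set is named.
- **After discontinuation.** The analysis section says that "the Investigator will ensure this does not affect the patient's standard of care" and that "The reasons for withdrawal will be recorded on the CRF and will be included in the final report". It does not say whether outcomes are collected or analysed.
- **Withdrawal of consent.** Participant consent provides that "the information about them and their donated tumor tissue that was collected before they left the study will still be used". This covers patients who withdraw consent, not those removed for an incomplete course.
- **Follow-up.** The Research Plan follows every study participant twice a year for 5 years. Outcome measure/study objectives follows every patient at 4-month intervals for 2 years and then twice a year. The two procedure charts (Figures 1 and 2) show follow-up of confirmed melanoma patients only.

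**The concern.** Completing both injections happens after randomization, and treatment can influence it. If patients who do not complete are left out, the arms compared are no longer the arms that were randomized. This applies to the TIL comparison and to metastasis alike.

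The trial is small enough for this to count: at the first planned analysis one removal is a tenth of an arm. The plan does not say whether a removed patient counts towards the 10 per arm, so the number analysed at that look is also open. Enrolment stops if that look is significant. Because the groups are unmasked at that point and no set is fixed beforehand, the choice of who is counted could be made once allocation is known.

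**Working it through.** **The plan's own figure.** The Research Plan expects significance with 20 patients (10 per arm). This cannot be reproduced: the documents give a two-sided 5% level and equal arms, but no effect size, SD, power, named test for TILs or dropout rate. For scale, 10 per arm with 80% power (assumed) detects √(2/10) × (1.960 + 0.842) = 1.25 SD by the normal formula, or 1.325 SD for a t-test.

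**One patient's leverage.** Removing one of 10 patients whose TIL score lies k SD from the arm mean moves the mean of the other nine by k/9. That is 0.11 SD for k = 1 and 0.22 SD for k = 2. The standard error of the difference is √(1/10 + 1/10) = 0.447 SD.

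**Illustration of selective removal.** The documents give no non-completion rate, so everything here is assumed: no true effect, 10 per arm, one pooled two-sided t-test at 5%, and 400,000 simulated trials per case. The 1, 2 or 3 IL-2 patients with the strongest reaction are removed, none on placebo, and reaction correlates 0.3 or 0.5 with TILs.

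| Correlation | Removed of 10 | Bias (SD) | Type I error | Favouring IL-2 | Against IL-2 |
|---|---|---|---|---|---|
| 0.3 | 1 | -0.05 | 5.2% | 2.0% | 3.2% |
| 0.3 | 2 | -0.09 | 5.5% | 1.6% | 3.9% |
| 0.3 | 3 | -0.14 | 5.8% | 1.3% | 4.5% |
| 0.5 | 1 | -0.09 | 5.5% | 1.7% | 3.8% |
| 0.5 | 2 | -0.16 | 6.5% | 1.2% | 5.3% |
| 0.5 | 3 | -0.23 | 7.5% | 0.9% | 6.6% |

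Repeat runs agree to within about 0.1 to 0.2 percentage points. Three variants set the limits:

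- Removal unrelated to TILs: no bias and about 5.0% type I error.
- The same selective removal in both arms: no bias and 5.1 to 5.8%.
- A correlation of opposite sign: by symmetry the bias favours IL-2, and false positives in its favour are 3.2 to 6.6% instead of 2.5%.

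**Power if non-completers are kept or dropped.** The assumed effect is 1.325 SD, and 2 of 10 IL-2 patients do not complete.

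| Handling | Power |
|---|---|
| Dropped (8 against 10) | 75% |
| Kept, full effect | 80% |
| Kept, half effect | 70% |
| Kept, no effect | about 55% |

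**Follow-up visits per retained patient.** Research Plan schedule: 2 × 5 = 10. Outcome measures schedule: 3 × 2 + 2 × 3 = 12.

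**The case against.** The strongest reply is that the text does not establish a comparison of completers. A reader might infer from the removal sentence that non-completers are left out of the analysis. But removal could mean removal from treatment, from visits or from analysis, and two sections promise follow-up of everyone. This objection stands: the documents support an undefined set and a conflict between sections, not a stated completers-only analysis.

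A reader might also infer that the outcome tissue is lost. It would usually exist, because the Lay Summary calls the excisional biopsy "part of the normal standard of care" and standard of care is protected after discontinuation. What is missing is a statement that the tissue is read and analysed for the trial.

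Third, removals may be few. The benefits and harms section expects mild symptoms that generally resolve within 48 hours, which is before Day 8. Both arms are injected under blinding, and no rule removes patients for reactions. The upper figures need three removals in one arm only, chosen by reaction. That stands too, and it limits the claim about size.

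Fourth, the simulated rates describe one look. The Research Plan allows five (20, 30, 40, 50 and 60 patients), and five unadjusted 5% t-tests with no removals already give about 12.9%. That is a separate and larger issue, and the rates above are not this trial's overall error.

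None of this supplies the missing definition. Nor does the analysis section's reference to a statistical-principles guideline, since citing a guideline does not say who is analysed.

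**Conclusion.** The point holds as an omission joined to a conflict, and should be fixed. A stated rule removes randomized patients before any post-treatment outcome, no analysis set is defined, and the sections disagree on who is followed. If removal means exclusion from assessment or analysis, the comparison loses the protection of randomization. The gap is confined to patients who miss an injection and keep their consent.

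Confidence is high for the omission but not for material bias. Under the assumptions shown, a single look ranges from near nominal (5.2%) to about 7.5%, and equal removal gives no bias. A reader might infer that the rule favours IL-2. The documents do not support any direction: the illustrated pattern works against IL-2, and its mirror image works for it.

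**What to change.** **Change.**

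1. In How will the data be analyzed, state that not completing both injections does not remove a patient from outcome assessment or analysis unless consent is withdrawn. Leave any rule on giving or stopping injections untouched.
2. Define the primary analysis set as all randomized patients in their assigned arm. Read TILs from the standard-of-care excision or biopsy and record its timing. Make completers of both injections a sensitivity analysis.
3. Report non-completers and missing TIL outcomes by arm. Reasons for withdrawal are already required, so only the breakdown is new.
4. State whether a non-completer counts towards the 10 per arm.
5. Reconcile the Research Plan, the two procedure charts, the outcome measures and the analysis section on who is followed.

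**Cost.** This is mainly wording. Keeping partly treated patients can dilute the effect: in the example above, power is 80%, 70% or about 55%, against 75% if they are dropped. Some TIL readings may fall on a day other than Day 15 and be less comparable, hence the recorded timing. Follow-up is 10 or 12 visits per retained patient, depending on the schedule. It adds little for confirmed melanoma, because the Research Plan describes that follow-up as identical to standard care.

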### What are the proposed benefits and potential harms of this research and how does the benefits outweigh the harms?:

Potential benefit: Generate an effective immune response to the patient's primary melanoma.

Risk-Breach of confidentiality; As with all research and sub-studies, there is a chance that confidentiality could be compromised; however, we are taking precautions to minimize this risk. All visits will be conducted in a private room to keep participant privacy.

Risk-Drug injections: Patients will be receiving an intralesional injection which may cause irritation and swelling at the site of injection. These discomforts are minimal and brief

Risk-Side effect of IL-2: Patients may feel mild flu like symptoms after receiving treatment, including fever, fatigue, headaches or muscle cramps. These symptoms are brief and general resolve within 48 hours

Risk-Drawing Blood; There is a possibility of pain, bruising, swelling or infection related to giving blood. These discomforts are minimal and brief.

Pregnancy/Fertility: FDA Pregnancy Category C. The effects of IL-2 on fertility and pregnancy is unknown and therefore pregnant women will be excluded from the trial and men and woman will be asked to use contraceptive protection during the two-week injection period.

Breastfeeding: it is not known whether IL-2 is excreted in human milk, therefore breastfeeding is contraindicated.

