#### Subject Selection:

Qualified dermatologists will identify and approach potential participants to recruit them to become part of the study. The participant population will include patients characterized by: nodular/polypoid features, bleeding/ulcerated lesions, excluding face and vulvo-genital lesions; and who are not: currently immunocompromized, on immuno-therapy for other diagnosis, have known inflammatory or autoimmune diseases or are otherwise incapacitated, between the ages of 18 and 80 years of age. We aim to include a minimum of 20 (up to 60) local participants over the next 24 months. Patients will be randomized and will receive a subcutaneous injection of either IL-2 treatment (treatment group) or the placebo PBS treatment (placebo group).

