This study is a randomized, controlled, double-blind study. Patients with highly suspicious pigmented lesions will be randomly assigned by an algorithm to one of two groups: 1) treatment group patients will be treated intralesionally with IL-2 (Proleukin (Aldesleukin), Novartis Pharmaceuticals Canada Inc.) at a dose of 500,000 International Units (IU) (0.1ml) for 2 treatment cycles 1 week apart (Day 1 and Day 8) Figure 1; 2) control group patients will be treated intralesionally with sterilized sodium chloride (0.9%, m/v) (0.1ml) Figure 1. Randomization will be done at the pharmacy for each patient (generated by a Random Block algorithm). IL-2 (Proleukin) will be obtained from the Provincial Drug Distribution Program by the pharmacy, paid for by [name] research services account (please see budget attached). The pharmacy will prepare either IL-2 treatment (supplied as 1 x 0.8ml (4 million units) or injectable placebo (0.9% sodium chloride) supplied as 0.8ml). The syringes will be prepared by following aseptic technique in a biohazard hood. A 22-million unit vial of IL-2 will be reconstituted with 1.2ml of sterile water for injection and mixed gently. After drawing up 3.2ml of 5% dextrose in water and transferring to the IL-2 vial, the resulting concentration will be 5 million units/ml. 0.8ml of the IL-2 solution will then be drawn into a 3ml syringe. Expiry time of the reconstituted solutions is 48 hours at 4C. The pharmacy will assign a codified ID which will be provided along with the syringe with the patient name labeled as "Interleukin-2/Placebo" (thus blinding study to clinician and patient). As a pilot study, the principle of the design is to test the feasibility of proceeding to a larger and more expensive trial following the methodology and protocol proposed. As such there will be a minimum of 20 (10 treatment, 10 placebo) participants (up to a maximum of 60). It is estimated that statistical significance will be reached with 20 patients, however it is not reached after 20 patients, an additional 10 (5 treatment, 5 control) patients will be enrolled. If significance is still not reached after 30 patients, an additional 10 patients will be enrolled and so on up to a maximum of 60 patients. If after 60 patients, significance is not achieved then further recruitment under the current protocol would not be logical and therefore the methodology would need to be revised or study discontinued.

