On Day 1 (first treatment) and 15 (excisional biopsy), all patients will have blood (4 vials) and urine (25-50 ml) samples taken. Local reactions to injections will be monitored for non-specific signs such as bleeding, arythema, infection, or irritation. We don't anticipate specific changes in the pigmented lesion related to the injection in this short time period, however all changes will be noted.

On Day 15, following the second intralesional injection an excisional biopsy will be performed following standard surgical techniques, as follows: ellipse of skin encompassing the pigmented lesion extending into the subcutaneous fat will be performed to achieve a grossly clear but narrow margin of excision. This small defect will be closed primarily with interrupted sutures. The biopsied specimen will be subsequently evaluated using standard histological techniques to confirm diagnoses, assess margin status (clear or involved) and depth of lesion invasion. The depth of lesion invasion will dictate the extent of subsequent surgical excisions and margin selection according to standard National Comprehensive Cancer Network (NCCN) guidelines. Pre-biopsy intralesional injections of 0.1ml into the lesion will not alter dimensions or architecture of the lesion or impact the extent the subsequent biopsy required. Lesions that are felt to be too large for closure without tissue manipulation or creation of flaps, will be biopsied using a punch biopsy sampling technique whereby 4mm diameter discs of tissue from representative areas of the lesion will be taken to confirm the diagnosis and the depth of invasion. The depth of invasion will dictate the extent and complexity of subsequent surgery required to remove the lesion and achieve clear margins according to NCCN guidelines. The biopsied specimen will be processed as follows: using a 22G needle a fine needle aspiration biopsy will be performed (the needle will be passed through the center of the lesion two times) for RNA analysis. The remainder of the tissue will be sent to pathology for standard histological assessment. The pathologist will also report the extent of observed tumor infiltrating lymphocytes (TILs) associated with treatment compared to control injections. Blood and urine will be assessed using metabalomic and proteomic methods to assess systemic immune response to treatment.

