All blood, urine, and lesion biopsy samples will be labeled with a codified number (will not contain any patient identifying information) and will be immediately transported to [name] laboratory (Sir Charles Tupper Medical Building, 11F11) at Dalhousie University for storage. Fine needle aspiration of excised samples will be assessed for tumor genetic and epigeneitic profile (Figure 2). Blood and urine will be assessed for proteomic and metabolomic profiles, respectively (Figure 2).

A database containing patient IDs and codified numbers will be restricted to the office of [name] (11th floor, VG). This is a locked office, and the data will only be accessible to the investigators named on this application. This database for will contain patient IDs, and info on disease status, treatment/control, follow up visits, and sample analysis – only info pertinent to the outcome measures. All sample data will be assessed using codified descriptors and will contain no patient ID info. Once the RNA, proteomic, metabolomic and pathology data has been analyzed, unmasking treatment and control groups will be conducted at the VG office of [name], by the named investigators. If the data reaches statistically significance, the study will not accept any more patients, if not, a further 10 patients will be incorporated – to a maximum of 60 patients. Any publications of study results will be completed devoid of any information that could be used to identify patients included in the study.

All study participants will receive biannual assessments for 5 years after the initial intervention to assess disease progression, or the development of new melanoma, to compare between both treatment and control groups. There is no standardize test or measurable biomarker to assess established or lasting immunity. This aspect of the study is identical to the patient assessment conducted as per standard of care for melanoma patients. Again, any publications of study results will be completed devoid of any information that could be used to identify patients included in the study.

	Interleukin 2 Treatment Group				
Interleukin-2 Treatment Group		Placebo Treatment Group			

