Day 1 Clinical Visit -Area of skin suspected of cancer photographed. -IL-2 treatment administered -Blood sampled – 4 tablespoons (60 ml) -Urine Sampled – 3 to 4 tablespoons (50 ml)		Day 1 Clinical Visit -Area of skin suspected of cancer photographed. -Placebo administered -Blood sampled – 4 tablespoons (60 ml) -Urine Sampled – 3 to 4 tablespoons (50 ml)			
Day 8 Clinical Visit -IL-2 treatment administered		Day 8 Clinical Visit -Placebo administered			
Day 15 Clinical Visit -Area of skin suspected of cancer photographed. -Blood sampled – 4 tablespoons (60 ml) -Urine Sampled – 3 to 4 tablespoons (50 ml)		Day 15 Clinical Visit -Area of skin suspected of cancer photographed. -Blood sampled – 4 tablespoons (60 ml) -Urine Sampled – 3 to 4 tablespoons (50 ml)			
-Surgical excision		-Surgical excision			
Confirmed melanoma patients -Follow up every 6 months for 5 years					
	
 
-Area of skin suspected of cancer photographed.
 
-IL-2 treatment administered
 
-Blood sampled – 4 tablespoons (60 ml)
 
-Urine Sampled – 3 to 4 tablespoons (50 ml)
 
 Day 8 Clinical Visit 
 
-IL-2 treatment administered
 
 Day 15 Clinical Visit 
 
-Area of skin suspected of cancer photographed.
 
-Blood sampled – 4 tablespoons (60 ml)
 
-Urine Sampled – 3 to 4 tablespoons (50 ml)
 
 Surgical excision Confirmed	
 
-Area of skin suspected of cancer photographed.
 
-IL-2 treatment administered
 
-Blood sampled – 4 tablespoons (60 ml)
 
-Urine Sampled – 3 to 4 tablespoons (50 ml)
 
 Day 8 Clinical Visit 
 
-IL-2 treatment administered
 
 Day 15 Clinical Visit 
 
-Area of skin suspected of cancer photographed.
 
-Blood sampled – 4 tablespoons (60 ml)
 
-Urine Sampled – 3 to 4 tablespoons (50 ml)
 
 Surgical excision Confirmed mela			

		Clinical and	Sub-s	study	Procedures
	Interleukin-2/Placebo Treatment Group			Sub-Study Process/Procedures	
Clinical Trial Procedures		Day 1 Clinical Visit -Area of skin suspected of cancer photographed -IL-2/Placebo treatment administered -Blood sampled – 4 tablespoons (60 ml) -Urine Sampled – 3 to 4 tablespoons (50 ml)			Day 1 Clinical Visit -Blood sample – To be used in proteomic sub- study (study of protein levels found in blood) -Urine Sample – To be used in metabolomic sub- study (study of metabolites released in urine)

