		Day 8 Clinical Visit -IL-2 treatment administered			Day 8 Clinical Visit -Nothing collected for sub-study at this visit
		Day 15 Clinical Visit -Area of skin suspected of cancer photographed -Blood sampled – 4 tablespoons (60 ml) -Urine Sampled – 3 to 4 tablespoons (50 ml)			Day 15 Clinical Visit -Blood sample – To be used in proteomic sub- study (study of protein levels found in blood) -Urine Sample – To be used in metabolomic sub- study (study of metabolites released in urine)
Standard of Care		-Surgical excision			-Biopsy sample collected from tissue removed during excision – To be used in RNA analysis sub- study (study of genes that may be involved in cancer development and growth)
Standa		-Confirmed melanoma patients Follow up every 6 months for 5 years			

Figure 2 Clinical and Sub-study Procedures

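### Pregnant women are excluded in the risk section only: Subject Selection omits pregnancy and breastfeeding, and no pregnancy test precedes the first IL-2 injection

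*Combined protocol and SAP*

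**What the plan says.** All references are to the combined protocol and SAP.

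- **Benefits and harms, Pregnancy/Fertility.** Because the effects of IL-2 on pregnancy are unknown, "therefore pregnant women will be excluded from the trial and men and woman will be asked to use contraceptive protection" over the two weeks of injections. The Breastfeeding entry below it calls breastfeeding contraindicated, without saying whether a breastfeeding woman is ineligible.
- **Subject Selection.** The criteria cover lesion features and sites, immune status, current immunotherapy, incapacity and age. The list ends with patients who "have known inflammatory or autoimmune diseases or are otherwise incapacitated, between the ages of 18 and 80 years of age". Pregnancy and breastfeeding do not appear, and there is no restriction by sex.
- **How will the data be analyzed.** Inclusion and exclusion criteria are settled at the baseline visit. Those who fail any of them are not entered, and randomization comes before the first treatment.
- **Research Plan.** "Randomization will be done at the pharmacy for each patient". On Days 1 and 15 "all patients will have blood (4 vials) and urine (25-50 ml) samples taken". The stated uses are proteomics for blood and metabolomics for urine. At Day 8 the sub-study column of Figure 2 reads "Nothing collected for sub-study at this visit".
- **Planned size.** "there will be a minimum of 20 (10 treatment, 10 placebo) participants (up to a maximum of 60".

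**The concern.** The plan sets a safety rule in its risk section but does not carry it into the criteria that staff check at baseline, or into any procedure that would detect a breach. Two problems follow. First, a person screening from Subject Selection alone would not be prompted to ask about pregnancy or breastfeeding. Second, even a person who knows the rule can apply it only by asking, and a woman who does not yet know that she is pregnant will answer no.

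What is at stake is exposure of a pregnancy to IL-2, which the plan itself sets out to prevent. This is a matter of participant safety and of enforcing eligibility. It does not bear on the analysis.

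**Working it through.** No formula applies and the plan gives no figure to reproduce. The check is a comparison of the relevant sections.

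1. **Is there an exclusion?** Yes, under Pregnancy/Fertility. The policy exists.
2. **Is it among the selection criteria?** No. Pregnancy and breastfeeding are mentioned only in the benefits-and-harms section.
3. **Can the population include women who could be pregnant?** Yes. Entry is open from age 18 without restriction by sex. The contraception request to women shows that the plan itself expects such participants.
4. **Does any supplied procedure test for pregnancy?** No. The visits described in the Research Plan and in Figures 1 and 2 consist of photography, injection, blood and urine sampling, and excision. The eligibility paragraph under the data analysis heading names no test either.
5. **Does the contraception request close the gap?** No. It covers the injection period, so it does nothing about a pregnancy already present on Day 1.
6. **What follows?** A known pregnancy can be caught by asking, provided that staff apply the risk section. An unrecognised one can pass the baseline check and be randomized. With 10 of the first 20 participants allocated to IL-2, such a woman would have a 10/20 = 1/2 chance of receiving it.
7. **How many tests would be needed?** At most one per participant, so no more than 20 at the minimum enrolment and 60 at the maximum. The actual number would be lower, since only women who could be pregnant need one.

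**The case against.** The strongest reply is that the policy is already in the protocol. Subject Selection is a short narrative paragraph rather than a formal criteria table, and the plan gives no verification procedure for its other exclusions either. On that view the omission is a cross-referencing gap, and contraindicated most naturally means that breastfeeding women are not enrolled. Consent follows a protocol approved by the research ethics board, and neither that protocol nor the consent pages were seen. Either could contain a screening step.

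Much of this stands. The policy is not missing, the breastfeeding part is mostly wording, and the absence of a test is established only for the supplied text. What survives is that pregnancy differs from the listed conditions in one practical way: a patient may be unaware of it while a simple test would show it. The inconsistency between the two sections remains whatever the consent pages say.

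A reader might go further and infer that the Day 1 urine could not be used for a test, because Figure 1 lists "IL-2 treatment administered -Blood sampled – 4 tablespoons (60 ml) -Urine Sampled – 3 to 4 tablespoons (50 ml" in that order, and because samples "will be labeled with a codified number (will not contain any patient identifying information) and will be immediately transported to" the research laboratory. The documents do not support this. The proteomic outcome needs serum from before and after treatment, yet blood is drawn only on Days 1 and 15. The pre-treatment sample must therefore be Day 1 blood taken before the first injection, although Figure 1 lists that blood after the injection as well. The list is thus not shown to be chronological. Prompt transport of coded samples does not prevent a strip test on site first.

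Nor do the documents place consent, screening and randomization all on Day 1. The Research Plan describes an initial consultation with two additional visits, so screening may come earlier. A rigid Day 1 sequence would go beyond what the plan says.

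**Conclusion.** The point holds as an inconsistency between two sections together with a missing enforcement step. As written, the baseline check can catch only a known pregnancy, and an unrecognised one could be randomized and exposed to IL-2.

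The probability is low in a trial of 20 to 60 participants. The documents give no distribution by sex or age and no pregnancy rate, so no expected count is claimed. No estimate, significance level or power changes. The case for acting is that the exposure is one the sponsor has chosen to exclude, and that preventing it costs little. The conclusion assumes that the consent pages, which were not seen, contain no pregnancy test. If they do, only the omission from Subject Selection remains.

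**What to change.** 1. Add pregnancy and breastfeeding to the exclusions under Subject Selection.
2. Require a negative urine pregnancy test in women who could be pregnant, either at the baseline visit or on Day 1 from a small part of the urine already being collected. The result should be read before randomization, and in any case before the first injection.

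This is a small protocol amendment. The cost is one test strip per woman who could be pregnant, a short wait for the result and, if Day 1 urine is used, a small aliquot of the sample. No visit is added. A pregnancy too early to detect would still be missed.
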